3.2 Implementation outcomes

- a) Acceptability of the intervention to women and health care professionals
- b) Feasibility of implementing the intervention

[figure not shown]

4 STUDY DESIGN

This study is a multicenter parallel, open label, superiority randomized controlled trial, with an alongside implementation study.

4.1 Study setting and site selection

The study will be undertaken in four states in Nigeria, two states in the North - Kano and Kwara states, and two in the South - Lagos and Rivers states. North-South differentials in the use of maternal health services, and in maternal health indices, such as lower ANC attendance and poorer maternal-infant outcomes in the North (14, 24, 25) necessitated representation of both regions in this study. The variation in indices across the four states strengthens the rationale for their selection. Lagos has the highest proportion of women with 4 or more ANC contacts as per the most recent guidelines of the World Health Organization. Kano has one of the least in the country while Rivers and Kwara reflect the average number of ANC contacts for many states in Nigeria. In terms of existing infrastructure, number of health facilities range from 994 in Kwara to 2,333 in Lagos (Figure 1).

Source of data for map: 2021 projected population by the National Bureau of Statistics, 2017 demographic Statistics Bulletin by National Bureau of Statistics, 2018 Nigerian Demographic Health Survey, 2020 Nigeria Health Facility Registry

Figure 1: Map of Nigeria indicating the four selected states for the study with key population and service indices

Five (5) health facilities at the three levels of health care (primary, secondary, and tertiary health facility) will be selected from each state for this study, making a total of twenty (20) study sites for this study (one tertiary, three secondary and one primary healthcare facility). The facilities are selected with consideration for antenatal patient flow, number of deliveries and proximity of all three levels of care to facilitate an effective two-way referral system (Table 1). Each state will have a Principal investigator (PI)

and each site will have a clinician as Site Coordinator (SC) and two research nurses. Eligibility criteria applied for site selection at all the states include:

- Exclusively publicly funded primary, secondary or tertiary health facility
- Presence of an antenatal clinic that serves at least 60 pregnant women per month and a labor ward that provides deliveries for at least 20 women per month
- Presence of a labor ward that provides consistent 24-hour vaginal delivery services

Table 1: Study sites and codes

Site code	State	Name of Study Site					
01	Lagos	Lagos University Teaching Hospital (LUTH), Idi-Araba, Lagos					

4.2 Study population

Postpartum women with moderate to severe iron deficiency anemia.

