1.1 Background

Anemia in pregnancy is a major public health burden with a high incidence in low- and middle-income countries (LMICs) such as Nigeria (1). It is most commonly caused by iron deficiency, which accounts for 50–75% (2). Postnatal anemia may result from untreated antenatal anemia or as a result of blood loss that occurs during birth. (3), and its prevalence in LMICs has been estimated to range from 50 to 80% (4). A study in Eastern Nigeria found anemia at 48 hours and six weeks postpartum to be 73% and 48% respectively, in a cohort of 202 women followed from late pregnancy until six weeks postpartum (5).

Anemia and iron deficiency anemia in pregnancy lead to increased morbidity and mortality for the mother and affects the neonates adversely (6). Specifically, postnatal anemia increases the risk of infection, leads to poor wound healing, and causes fatigue and depression in the mother (7). It also adversely affects breastfeeding, due to insufficient milk production, can reduce bonding between women and their newborn as a result of weakness and fatigue (3, 4, 8).

Oral iron is used routinely for the treatment of mild to moderate anemia in the postnatal period, while blood transfusion is offered for severe anemia or symptomatic women with moderate anemia (3). Oral iron, though inexpensive, causes significant gastrointestinal adverse effects such as vomiting, constipation, diarrhea, and abdominal pain (9), limiting adherence to this vital intervention which may pose a challenge in achieving optimum correction of anemia by the end of the postnatal period. Adherence to oral iron is reportedly low, with only 16% of women fully compliant with their treatment in a study among pregnant women in Cameroon, one of Nigeria's neighboring countries (10).

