There are many safe parenteral iron preparations, such as iron sucrose, iron polymaltose, ferric carboxymaltose and iron isomaltoside, with few adverse effects (16). Ferric carboxymaltose is safe and effective but was recently found to reduce serum phosphate levels (17). However, the associated reduction in serum phosphate concentration is not thought to be clinically relevant in pregnancy, probably because it is given in just a few doses. In studies conducted in pregnant women, the serum phosphate has been found to return to normal within a short period of time (18-20). The main disadvantage with intravenous iron preparations is that they are relatively expensive (16) but as they offer the potential to avoid blood transfusion and its complications and reduce maternal morbidity and mortality this cost might be mitigated.

As postpartum anemia is highly prevalent in Nigeria and has a significant detrimental impact on the physical and mental health of women and their newborns, we propose a randomized controlled trial examining the clinical effectiveness of intravenous ferric carboxymaltose versus oral ferrous sulphate for moderate to severe anemia in postpartum Nigerian women. Recognizing the volatility of introducing such treatment in Nigeria, we also propose an alongside implementation study to better understand the implementation climate and assess key implementation outcomes.

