2 STUDY OBJECTIVES

2.1 Aims

- a) To determine the clinical effectiveness, tolerability, and safety of intravenous ferric carboxymaltose (intervention) versus oral ferrous sulphate (control) for treating moderate to severe iron deficiency anemia in postpartum women (population).
- b) To evaluate implementation of intravenous ferric carboxymaltose in treating postpartum anemia in Nigeria.

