4.2.1 Selection of participants

Inclusion criteria:

- a) Women aged between 15 and 49 years.
- b) Between six and 48 hours after delivery. A minimum of six hours has been chosen because we expect the initial post-birth blood loss to have subsided and the hemoglobin concentration to be sufficiently representative of the true hemoglobin concentration at that time; 48 hours has been chosen as the upper limit for pragmatic reasons because women are usually discharged from hospital after 48 hours.
- c) Baseline (enrollment) moderate or severe anemia (**Hb≤9.9g/dl**), confirmed by Hemocue haemoglobinometer.
- d) Able and willing to give written informed consent.

Exclusion criteria:

- a) Having received a blood transfusion, for any indication, within the last three months.
- b) Symptomatic anemia and a need for urgent correction.
- c) Known haemoglobinopathy such as sickle cell disease, HbCC disease.
- d) Clinically confirmed malabsorption syndrome.
- e) Known hypersensitivity or contraindication to any form of iron treatment, study drug or any of its excipients.
- f) Self-reported pre-existing maternal depression or other psychiatric illness and as evidenced by a YES response to Any Past history of Psychiatry ward hospitalization, Psychiatry medications, behavioral changes, or past consultation with Psychiatry services.
- g) Severe allergic conditions such as severe asthma, eczema, or other atopic condition.
- h) Known autoimmune conditions e.g., systemic lupus erythematosus, rheumatoid arthritis or known severe drug allergies.
- i) Planning to move or reside outside the research area
- i) Women who have had intravenous iron administered in the last two years (26).

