4.10.1 Screening & and consent (visit 0)

- The required information from this visit will be completed for all prospective participants in the *screening log* (Appendix v).
- All prospective participants are women who are within six and 48 hours after delivery.
- These women will be assessed using the study eligibility criteria (inclusion and exclusion)
- Those that meets the eligibility criteria will then have their hemoglobin concentration determined using the POCT haemoglobinometer. Complete the *Hb check worksheet* as appropriate.
- Participants with *Hb* ≤9.9g/dL who have been determined to meet other study eligibility criteria are then consented for participation in the study.
- Informed consent must be obtained at this visit when the prospective participant meets ALL study eligibility criteria.

The **informed consent process** is described below:

- The research nurse assistant will provide the full participant's information sheet to the prospective participant. Information will be disclosed to the prospective participant, and it will be ensured she comprehends the nature and purpose of the study, duration of participation, procedures to be done, community tracking as necessary including home visitations and laboratory investigations to be performed. She should also be made aware of any foreseeable risk and discomfort, other study requirements and visits schedule, participants' responsibility and be willing to freely participate.
- Acceptance/rejection to participate
- Agreement to participate (Consent) must be recorded (written) and witnessed where necessary. Each participant will be asked to sign (or provide other mark such as thump print if need be) *three copies* of an *informed consent document* (*Appendix vi*), in English or translated into Yoruba/Hausa/Igbo as appropriate. The participant will be given a signed copy to take home. If the participant cannot read, a witness must be present at the time of the information disclosure and consent process and will witness the signature or mark of the participant.

If a prospective participant is screened but does not get enrolled, the reason for not being enrolled must be documented in the screening log.

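### The stated population is iron deficiency anemia, but women enter on hemoglobin alone, so the primary result by itself speaks only to postpartum anemia of any cause

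*Protocol*

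**What the plan says.** Four places in the protocol name the population as iron deficiency anemia: the synopsis (aims and objectives), section 2.1, section 2.2 and section 4.2. Section 2.1(a) labels it explicitly: "for treating moderate to severe iron deficiency anemia in postpartum women (population". Section 4.2 reads "Postpartum women with moderate to severe iron deficiency anemia".

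The entry criteria directly below, in section 4.2.1, ask for "Baseline (enrollment) moderate or severe anemia", set at Hb 9.9 g/dl or less and "confirmed by Hemocue haemoglobinometer". No inclusion or exclusion criterion uses an iron marker. Some other causes of anemia are filtered, for example "Known haemoglobinopathy such as sickle cell disease, HbCC disease", but only where already known.

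Section 1.1 attributes much, but not all, anemia in pregnancy to iron deficiency: "It is most commonly caused by iron deficiency, which accounts for 50–75" per cent. The same section then frames the trial without iron deficiency, as intravenous iron "versus oral ferrous sulphate for moderate to severe anemia in postpartum Nigerian women".

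Section 4.9 and Table 3 schedule a full iron panel at enrollment. Section 9.4 names two subgroup factors, mode of delivery and primary postpartum hemorrhage. None of the analysis sets in section 9.3 is defined by iron status.

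**The concern.** The protocol describes two different populations. A primary result reported under the aims as written would be attached to iron deficiency anemia, although the trial does not select for it. A reader could then take an all-cause anemia result as evidence about iron deficiency.

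There is also a question of interpretation. If the overall effect is small, one candidate explanation is that some women were not iron deficient. A split by iron status chosen after the data are seen would be weak evidence for that explanation, and the protocol names no such split in advance.

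**Working it through.** **Can iron status act as an entry filter?** The visit steps show that it cannot.

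- Section 4.10.1: women at or below the Hb threshold "who have been determined to meet other study eligibility criteria are then consented for participation in the study". No iron result is called for.
- Section 4.10.2: randomization is step 1. Blood sampling is listed later, followed by the study drug.
- Section 4.9: everything except point-of-care tests goes to an external laboratory.

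The enrolled population is therefore defined by hemoglobin. Because the enrollment sample is listed before the study drug, the panel can still serve as a true baseline variable.

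**Does the protocol expect other causes?** Yes. Section 1.1 leaves 25% to 50% of anemia in pregnancy to other causes, and section 5.2 provides for evaluating other forms of anemia when treatment fails.

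**Inputs for power (section 4.3).** 39% anemic on control, 30% on intravenous iron, 697 per arm, 10% loss, 90% power; then 700 per arm at final alpha 0.0492. Tests are two-sided (section 9.4).

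**Formula.** Power = Φ{[|p1 − p2| − z·√(2p̄(1 − p̄)/n)] / √([p1(1 − p1) + p2(1 − p2)]/n)}, where p̄ is the mean of p1 and p2 and z is the two-sided critical value.

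**The plan's own figure.**

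- 697 × 0.90 ≈ 627 evaluable at alpha 0.05: power 91.9%.
- 700 × 0.90 = 630 evaluable at alpha 0.0492 (z = 1.967): (0.0900 − 1.967 × 0.02678)/0.02666 = 1.40, power 91.9%.

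Both agree with the stated 90%. Solving for sample size gives a looser match: 585 evaluable, or 650 enrolled per arm, against the stated 697.

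**What dilution would do, under assumptions the protocol does not state.** Let s be the iron-deficient share of enrolled women and k the fraction of the 9-point effect that the other women receive. Assume the same 39% control rate in both groups. The overall difference is 9 × [s + (1 − s)k] points. With n = 630 and alpha 0.0492:

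| Scenario | Difference (points) | Treated rate | Power |
|---|---|---|---|
| 39% vs 30% already describes unselected anemia | 9.0 | 30.0% | 92% |
| s = 75%, k = 0.5 | 9 × 0.875 = 7.875 | 31.1% | 83% |
| s = 50%, k = 0.5 | 9 × 0.75 = 6.75 | 32.25% | 70% |
| s = 75%, k = 0 | 9 × 0.75 = 6.75 | 32.25% | 70% |
| s = 50%, k = 0 | 9 × 0.50 = 4.5 | 34.5% | 38% |

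**Comparison within iron-deficient women** (39% vs 30%, alpha 0.05):

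- s = 75%: 630 × 0.75 = 472.5 per arm, power 83%.
- s = 50%: 630 × 0.50 = 315 per arm, power 66%.

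**Interaction on the risk-difference scale, k = 0.** The variance is (0.39 × 0.61 + 0.30 × 0.70)/(630s) + 2 × 0.39 × 0.61/(630(1 − s)).

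- s = 75%: z = 1.43, power about Φ(1.43 − 1.96) = 30%.
- s = 50%: z = 1.66, power about Φ(1.66 − 1.96) = 38%.

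The interaction test can support interpretation but cannot decide the question.

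**The case against.** **Selecting on hemoglobin is defensible.** Entry closes at 48 hours, sites include primary care, and iron assays go to an outside laboratory. This stands. The point concerns the label on the population, not the entry rule.

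**Subgroups and ferritin cut-offs commonly belong in a SAP, which is not at hand.** This stands in part. Section 9.4 models iron biomarkers over time, compares proportions iron deficient, and allows unnamed baseline covariates, so the absence of an iron-status subgroup is not in itself an error. But population, aims and eligibility are protocol content, and a SAP cannot reconcile section 4.2 with section 4.2.1.

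**Two stronger readings are tempting, and the documents do not support either.**

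- A reader might infer that the trial cannot support its stated conclusion at all. The randomized comparison remains valid for women with Hb of 9.9 g/dl or less, and the enrollment panel makes an analysis in iron-deficient women possible.
- A reader might infer that the effect is diluted as a matter of fact. That needs three things the protocol does not establish: that the 50–75% share, given for anemia in pregnancy, applies to this postpartum cohort after its exclusions; that women without iron deficiency benefit less; and that 39% versus 30% describes iron-deficient women only. Section 4.3 takes the 39% from a meta-analysis without saying how its women were selected. If the planning figures describe unselected postpartum anemia, there is no further dilution.

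**Conclusion.** The contradiction between the stated population and the entry criteria is real and can be checked on the page. It depends on no assumption. As planned, the primary result supports a statement about moderate to severe postpartum anemia of any cause. A statement about iron deficiency anemia needs an additional analysis.

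Dilution is a conditional risk. Power for the overall test ranges from 92% (no dilution) to 38% (half the women deficient, no effect in the rest), with 70% to 83% in the intermediate cases. The range rests on a common 39% control rate, on 630 evaluable women per arm, and on borrowing the pregnancy share of 50–75% for this cohort.

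**What to change.** 1. In the synopsis and sections 2.1, 2.2 and 4.2, restate the population as moderate to severe postpartum anemia (Hb 9.9 g/dl or less) regardless of iron status, and word the conclusions to match.
2. In section 4.3, state which population the 39% versus 30% assumption describes.
3. Pre-specify, as a supportive analysis for the iron deficiency objective, the primary-endpoint comparison in women who are iron deficient on the enrollment panel, together with the treatment-by-iron-status interaction. Fix the definition and cut-offs before any unblinded look, including the interim analysis.

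Eligibility, treatment and sample size do not change, and the data are already scheduled. The cost is that the headline claim becomes anemia rather than iron deficiency anemia. The supportive comparison also has less power than the planned 92%: about 83% at a 75% share and 66% at 50%, and the interaction test has less still.

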4.2.1 Selection of participants

Inclusion criteria:

- a) Women aged between 15 and 49 years.
- b) Between six and 48 hours after delivery. A minimum of six hours has been chosen because we expect the initial post-birth blood loss to have subsided and the hemoglobin concentration to be sufficiently representative of the true hemoglobin concentration at that time; 48 hours has been chosen as the upper limit for pragmatic reasons because women are usually discharged from hospital after 48 hours.
- c) Baseline (enrollment) moderate or severe anemia (**Hb≤9.9g/dl**), confirmed by Hemocue haemoglobinometer.
- d) Able and willing to give written informed consent.

Exclusion criteria:

- a) Having received a blood transfusion, for any indication, within the last three months.
- b) Symptomatic anemia and a need for urgent correction.
- c) Known haemoglobinopathy such as sickle cell disease, HbCC disease.
- d) Clinically confirmed malabsorption syndrome.
- e) Known hypersensitivity or contraindication to any form of iron treatment, study drug or any of its excipients.
- f) Self-reported pre-existing maternal depression or other psychiatric illness and as evidenced by a YES response to Any Past history of Psychiatry ward hospitalization, Psychiatry medications, behavioral changes, or past consultation with Psychiatry services.
- g) Severe allergic conditions such as severe asthma, eczema, or other atopic condition.
- h) Known autoimmune conditions e.g., systemic lupus erythematosus, rheumatoid arthritis or known severe drug allergies.
- i) Planning to move or reside outside the research area
- i) Women who have had intravenous iron administered in the last two years (26).

4.3 Sample size

We will enroll 1400 women into the trial. Power calculations assume a 1:1 randomization ratio to each of the two treatment groups.

For the primary outcome (anemia), we used data from a recent meta-analysis (28), which reported that 39% of women were anemic at six weeks postpartum. A sample size of 697 participants per arm would

^{**}A prospective participant with chronic medical condition (e.g HIV infection) will not be excluded unless there are contra-indication for the use of iron supplementation.

provide 90% power to detect to detect a relative reduction of 20% for IV iron to reduce the event rate of anemia at six weeks postpartum to 30%, after accounting for 10% loss to follow-up.

Bearing in mind the proposed one-time interim analysis to be conducted by the Data and Safety Monitoring Board (DSMB) at mid recruitment, we applied the O'Brien-Fleming rule (29), adjusting our final alpha level to 0.0492 (*See section 9.3 for interim rule*), which increased our final sample size to 1400 (700 per arm of the study).

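### Section 4.3 gives two different effects as one: the 90% power holds for 39% vs 30% (a 23% relative reduction), but power is only about 82-83% for the stated 20% relative reduction (39% vs 31.2%)

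*Protocol*

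**What the plan says.** Protocol section 4.3 (Sample size) contains the trial's only power statement. The control rate comes from a meta-analysis, "which reported that 39% of women were anemic at six weeks postpartum". The protocol then says: "A sample size of 697 participants per arm would" "provide 90% power to detect" "a relative reduction of 20% for IV iron to reduce the event rate of anemia at six weeks postpartum to 30"%, which gives the relative and the absolute form as the same effect. The figure is given "after accounting for 10% loss to follow-up". Allocation is 1:1. One interim analysis lowers the final alpha to 0.0492, and the protocol raises the size to 1,400, or 700 per arm.

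Section 9.4 (Data analysis plan) specifies two-tailed tests. The primary analysis is a log-binomial model that reports a relative risk with a 95% confidence interval. The same section allows an interim re-assessment of the sample size.

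**The concern.** The relative and absolute descriptions of the effect cannot both be true when the control rate is 39%. Rounding does not reconcile them: 31.2% rounds to 31%, and 23.1% does not round to 20%. One sample size cannot give the same power for both, so the 90% can belong to at most one of them.

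This matters because the primary effect measure is a relative risk, so the 20% figure is the one a reader will set beside the result. Anyone who takes section 4.3 at its word will believe that the trial had a 10% chance of missing a relative risk of 0.80. If the true chance is larger, the protocol misstates what the trial can detect.

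**Working it through.** **Inputs.** From section 4.3: control rate 0.39; treated rate either 0.30 or 0.39 × 0.80; power 0.90; 697 per arm before and 700 per arm after the interim adjustment; 10% loss; alpha 0.05 before and 0.0492 after the adjustment; 1:1 allocation. From section 9.4: two-sided testing.

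**Step 1: the two effects.**
- 0.39 × 0.80 = 0.312, a difference of 7.8 points.
- 1 − 0.30/0.39 = 0.231, a difference of 9 points.

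**Step 2: evaluable women.** 697 × 0.9 ≈ 627 per arm; 700 × 0.9 = 630 per arm.

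**Step 3: formula.** Two-proportion normal approximation with pooled null variance:

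power = Φ( [√n·|p1 − p2| − z(1−α/2)·√(2p̄(1−p̄))] / √(p1(1−p1) + p2(1−p2)) ), where p̄ = (p1 + p2)/2.

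For α = 0.0492, z = 1.967. For n = 630, √n = 25.10.

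**Step 4: the protocol's own figure, 39% vs 30%.** p̄ = 0.345. The null term is 0.6723 and the alternative term 0.6693.
- n = 630, α = 0.0492: (25.10 × 0.09 − 1.967 × 0.6723)/0.6693 = 1.40, so power is 91.9%.
- n = 627, α = 0.05: also 91.9%.
- With continuity correction, n = 630, α = 0.0492: 91.0%. On the log relative risk scale: 91.4%.

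The stated 90% is met for the 30% target.

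**Step 5: the stated 20% relative reduction, 39% vs 31.2%.** p̄ = 0.351. The null term is 0.6750 and the alternative term 0.6727.
- n = 630, α = 0.0492: (25.10 × 0.078 − 1.967 × 0.6750)/0.6727 = 0.937, so power is 82.6%.
- n = 627, α = 0.05: 82.6%.
- With continuity correction, n = 630, α = 0.0492: 81.0%. On the log relative risk scale: 82.1%.

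The type II error is about 17-18% (19% with continuity correction), against the 10% implied.

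**Step 6: size needed for 90% power.** n = [(z(1−α/2)·null term + 1.2816·alternative term)/|p1 − p2|]², then divided by 0.9 for loss.

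| Target | α | Evaluable per arm | Enrolled per arm | With continuity correction, enrolled per arm |
|---|---|---|---|---|
| 30% | 0.05 | 585 | 650 | 675 |
| 30% | 0.0492 | 587 | 653 | 677 |
| 31.2% | 0.05 | 785 | 873 | 902 |
| 31.2% | 0.0492 | 789 | 877 | 905 |

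For 31.2% at α = 0.0492 the total is 2 × 877 = 1,754, or 1,810 with continuity correction.

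**Step 7: what 697 corresponds to.** With 627 evaluable per arm and α = 0.05, 90% power is reached at 39% vs 30.3%, a 22.3% relative reduction. With 630 and α = 0.0492 the answer is again 30.3%. The 697 also lies about 3% above the continuity-corrected size for 30% (675-677). No two-sided variant tried brings 697 near the requirement for 31.2%.

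**The case against.** The best defence is that the design was built on the 30% target and only the relative percentage was misprinted. The arithmetic supports this. Power for 39% vs 30% is 91-92%. The 697 fits a target of about 30.3%, which would print as 30%, and it is close to the continuity-corrected size for exactly 30%. Section 4.3 does not name its formula, so the excess over the uncorrected 650 is conservative and no defect. All of this stands.

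It rules out a stronger reading that a reader might infer, that the 90% belongs to neither stated effect or that 697 cannot be derived from either. For the 30% target the documents do not support that.

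A reader might also infer that the wrong effect will feed the sample-size re-assessment. Section 9.4 says only that the re-assessment will look at the actual effect size of the primary outcome. It does not name the 20% figure as an input, so that harm is not documented.

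A third stronger reading is that a null result would be taken to exclude a 20% reduction. Section 9.4 plans a relative risk with a 95% confidence interval, and what the data exclude will be read from that interval.

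Finally, no outcome, boundary or analysis rule uses the 20% figure, and the protocol gives no clinical reason for preferring 20% to the 9-point difference. The shortfall therefore depends on which half of the sentence was meant. That limits the consequence but does not remove the error: the sentence attaches 90% power to an effect for which the design does not have it. A one-sided 0.05 test would bring the size for 31.2% to about 704-712 per arm, near 697, but section 9.4 specifies two-tailed tests.

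**Conclusion.** The point holds in limited form. Section 4.3 contradicts itself on the effect size, and its 90% power is correct for only one of the two effects it states. For 39% vs 30% (23.1% relative) power is about 92%, or 91% with continuity correction. For the stated 20% relative reduction (39% vs 31.2%) it is about 82-83%, or 81% with continuity correction, and 90% would need about 1,750 women, some 350 more than planned.

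These figures assume the 39% control rate, exactly 10% loss in each arm, independent observations and two-sided alpha 0.0492 at the final analysis. They do not show that the trial is too small. If 30% was the intended target, 1,400 is adequate and only the text is wrong. If a 20% relative reduction was intended, the trial falls short of its own stated power. The protocol does not let a reader tell which, so the sentence must be corrected.

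**What to change.** Keep 1,400 women and rewrite the power statement in section 4.3 around one consistent effect. For example: 630 evaluable women per arm give about 92% power for 39% vs 30% (9 points, 23% relative reduction) and about 82% power for a 20% relative reduction (39% vs 31.2%), at two-sided alpha 0.0492. Name the formula used, so that 697 and 700 can be reproduced. If the sample-size re-assessment in section 9.4 uses a target effect, it should be the corrected one.

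The cost is an amendment to the wording of section 4.3. No extra women, visits or analyses are needed. The sponsor must accept a less favourable power figure for the 20% reduction.
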